8.2. Right Heart Catheterization and Implant Procedure (Baseline Visit)

Before the RHC, the following procedures/assessments will be performed:

- Abbreviated physical examination (i.e., vital sign assessments and significant changes since Screening Visit) and weight
- Confirmation of enrollment eligibility (other than angiographic criteria)
- PT/PTT with International Normalized Ratio (INR) of 1.5 or less for subjects previously on warfarin
- Assessment of heart failure medications
- Record any medical history updates since screening visit.

This confidential document is the property of Abbott and shall not be reproduced, distributed, disclosed or used without the express written consent of Abbott

Clinical Investigation Plan

The patient will then undergo a standard RHC. A selective, hand injected pulmonary angiogram will be performed via the pulmonary artery catheter to identify a suitable pulmonary artery branch for sensor implantation. Subjects must have an appropriately sized ($\geq 7\text{mm}$ diameter) pulmonary artery branch. Subjects who do not meet this inclusion criteria will not receive the PA Sensor implant and will be considered ineligible for the study. These subjects will be documented as consented not implanted and will be followed for 30 days for safety. Patients with a suitable target pulmonary artery branch will undergo:

- Wireless implantable hemodynamic sensor implant
- Pulmonary artery catheter measurements (pulmonary systolic, pulmonary diastolic, pulmonary mean, cardiac output) done 3 times consecutively with sensor measurements for setting of sensor baseline.
- Provide post-procedure vascular access site care per standard procedure
- At the Investigator's discretion, subjects should be discharged once stable with respect to the procedure and their heart failure.
- Please see User's Manual for implant details

Subjects who are currently on anticoagulant therapy (warfarin, or any FDA approved anticoagulant) will restart treatment. The subject's INR should be checked periodically to ensure that it is in the therapeutic range. Those subjects not on chronic warfarin will be placed on anticoagulant/antiplatelet therapy as indicated in the device User's Manual. Refer to the User's Manual for further details.

8.3. Study Follow-Up Visits 1, 2, 3, 4, and 5 (Months 1, 6, 12, 18, and 24)

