8.5. PA Pressure Readings in the Hospital

If a subject is hospitalized, seen in the emergency room (ER) or has a clinic visit, the CardioMEMS HF System may be used to obtain pulmonary artery pressure measurements at the investigators discretion. Following sensor implant, subsequent RHC procedures or pulmonary artery catheter insertions must be performed under fluoroscopic guidance.

Resetting of the sensor baseline will be performed as deemed necessary by Sponsor. Baseline resetting may require an echocardiogram or a RHC procedure.

Following the sensor implant, should a RHC procedure or PA catheter evaluation be clinically warranted, comparative pulmonary artery pressures utilizing the CardioMEMS HF System should also be obtained utilizing the hospital electronics unit.

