9.1.2. Sensor Failure Criteria

A Sensor failure occurs when no readings can be obtained from it after troubleshooting the system to rule out any problems with the external electronics.

EFFECTIVENESS ANALYSES

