	Subjects	Events	Subjects	Events	Subjects	Events	Subjects	Events
All Patients with an Event	XX (XX.X%)	XXX	XX (XX.X%)	XXX	XX (XX.X%)	XXX	XX (XX.X%)	XXX
System Organ Class I	XXX	XXX	XXX	XXX	XXX	XXX	XXX	XXX
...								

Days alive outside of hospital for heart failure

	6 Months N=XXXX	12 Months N=XXXX	18 Months N=XXXX	24 Months N=XXXX
	N	N	N	N
Days Alive outside of Hospital	XXX	XXX	XXX	XXX

Weekly Patient Pressure Reading Compliance

	Compliance %
Mean \pm StdDev	XX.X \pm XX.X%
Median	XX.X%

Sensor Performance

	N	Percent
Number of Patients	XXX	XX.X%
Number of RHCs with comparative readings	XXX	XX.X%

Results will be presented using Bland-Altman comparing Sensor vs. Swan-Ganz.

Clinical Investigation Plan

[figure not shown]
Medication changes in response to PA pressure

Medication Changes in Response to PA Pressure	# Medications	
	N	Percent
ACE/ARB	XXX	XX.X%
Aldosterone Antagonist	XXX	XX.X%
Beta-blocker	XXX	XX.X%
Diuretic-Loop	XXX	XX.X%
Diuretic-Thiazide	XXX	XX.X%
Hydralazine	XXX	XX.X%
Nitrate	XXX	XX.X%
Other	XXX	XX.X%
Total	XXX	XX.X%

This confidential document is the property of Abbott and shall not be reproduced, distributed, disclosed or used without the express written consent of Abbott

Clinical Investigation Plan

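### Sensor accuracy is planned only as a Bland-Altman comparison, with no split by time since implant and no method for repeat catheterizations, so drift in a sensor that still transmits is not estimated

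*Combined protocol and SAP*

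**What the plan says.** The Sensor Performance block of Appendix L has two rows, one for patients and one labelled "Number of RHCs with comparative readings", with columns for count and percent. One sentence of method follows: "Results will be presented using Bland-Altman comparing Sensor vs. Swan-Ganz". The text names no time window, no pressure (systolic, diastolic or mean), no agreement limit and no way of handling several pairs from one patient. A figure follows it that is not reproduced in the text available for review. Section 12 contains no accuracy analysis.

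Other parts of the plan bear on this:

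- The Appendix L tables for safety, HF hospitalization, mortality, SAEs and days alive have columns headed "6 Months N=XXXX 12 Months N=XXXX 18 Months N=XXXX 24 Months N=XXXX". Sensor Performance does not.
- Section 8.2 takes catheter measurements at implant "done 3 times consecutively with sensor measurements for setting of sensor baseline".
- Section 8.5 makes later comparisons unscheduled: "Following the sensor implant, should a RHC procedure or PA catheter evaluation be clinically warranted, comparative pulmonary artery pressures utilizing the CardioMEMS HF System" are to be obtained as well.
- Section 8.5 also says: "Resetting of the sensor baseline will be performed as deemed necessary by Sponsor".
- Section 9.1.2 defines the safety endpoint: "A Sensor failure occurs when no readings can be obtained from it" once faults in the external electronics have been ruled out.

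**The concern.** A Bland-Altman display sets the difference between two methods against their mean. Time since implant is on neither axis. For a permanent sensor followed for 24 months, a natural post-approval question is whether it still agrees with the catheter late in follow-up, and the planned summary does not address that as worded.

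No other analysis fills the gap. A sensor that transmits a wrong pressure is not a failure under Section 9.1.2. The six-monthly updates do not supply the split either. They follow study calendar time, while Appendix A spreads enrollment over 37 study months, so each update mixes new and old implants.

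Two features could also hide drift. Implant-day pairs are used to set the baseline, so they agree largely by construction, and the plan does not say whether they enter the comparison. A baseline reset removes accumulated offset from later pairs, and the plan does not say how pairs before and after a reset are treated.

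At stake is how far the sensor-performance report can be relied on. It goes to FDA and into the device labeling (Section 14), and Appendix D has sites act on the transmitted pressures.

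**Working it through.** The plan states no sample size, precision or agreement limit for accuracy, so there is no figure to reproduce. What follows shows how a summary that ignores time would behave.

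**Inputs.** From the documents: 24 months of follow-up, unscheduled RHCs, resets allowed. Assumed, because the documents give nothing: linear drift of d = 0.5 to 2 mmHg per year, SD of the sensor-minus-catheter difference s = 3 or 5 mmHg, no resets, and RHC times t either uniform on 0 to 2 years or with a mean of 0.5 year.

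**1. Drift common to all sensors.** True bias at month 24 is 2d. Pooled bias is d × E[t].

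- Uniform times: E[t] = 1, so pooled bias is d, and d/2d = 1/2.
- Mean time of 6 months: E[t] = 0.5, so pooled bias is 0.5d, and 0.5d/2d = 1/4. The same ratio arises if half the pairs are implant-day readings and the rest are uniform, since 0.5 × 0 + 0.5 × 1 = 0.5.

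The half-width of the pooled limits under uniform times is 1.96 × √(s² + d²/3), because Var(t) = 4/3 − 1 = 1/3. With s = 3 and no drift it is 1.96 × 3 = 5.88.

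| d (mmHg/year) | Bias at month 24 | Pooled bias, uniform | Pooled bias, mean 6 months | Pooled limits, uniform, s = 3 |
|---|---|---|---|---|
| 0.5 | 1 | 0.5 | 0.25 | ±5.91 |
| 1 | 2 | 1 | 0.5 | ±5.99 |
| 2 | 4 | 2 | 1 | ±6.30 |

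The limits barely move, so they would not reveal a common drift. For scale, the Appendix D range for PA diastolic pressure is 8 to 20 mmHg.

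**2. Drift of mixed sign.** Let the drift rate vary between sensors with mean 0 and SD d. Pooled bias is 0. Under uniform times the pooled half-width is 1.96 × √(s² + 4d²/3), since E[t²] = 4/3. At month 24 it is 1.96 × √(s² + 4d²).

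- s = 3, d = 2: pooled 1.96 × √14.33 = 7.42; month 24 1.96 × √25 = 9.80; no drift 5.88.
- s = 5, d = 2: pooled 1.96 × √30.33 = 10.79; month 24 1.96 × √41 = 12.55; no drift 9.80.

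The limits widen, but not to their month-24 size.

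**3. Repeat pairs.** With m pairs per patient, within-patient correlation ρ and N pairs in all, balanced across patients, the ordinary variance has expectation σ²(N − DE)/(N − 1), where DE = 1 + (m − 1)ρ. Take N = 100 (assumed).

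- m = 2, ρ = 0.5: DE = 1.5, √(98.5/99) = 0.9975, so the limits are 0.25% too narrow.
- m = 3, ρ = 0.9: DE = 2.8, √(97.2/99) = 0.991, so the limits are 0.9% too narrow.

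At N = 30 the second case gives √(27.2/29) = 0.968, or 3.2%. Repeat pairs are therefore a minor issue for balanced limits. If repeats are unbalanced, the patients catheterized most often carry the most weight.

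**The case against.** **The text is silent rather than wrong.** A reader might infer that every comparison goes into a single plot. The documents do not say so, and the figure that follows could show several panels. This stands: the point is only that the visible text specifies no time split and no repeated-measures method.

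**Drift would not vanish.** A reader might infer that drift is averaged away. The working shows otherwise. Common drift remains as a reduced bias, and drift of mixed sign still widens the limits. It is diluted and cannot be separately estimated.

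**Misreading sensors could be recorded elsewhere.** Section 11.6.2 lists sensor failure/malfunction among anticipated device effects, Section 12.6.1 tabulates device effects, and Section 11.4 provides for reporting device deficiencies. That is a route for recording a case, but it does not estimate drift.

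**Repeat pairs hardly matter.** A reader might infer that they make agreement look markedly more precise than it is. That would apply to a confidence interval for mean bias, which the plan does not mention. For balanced limits of agreement the effect is small, as shown.

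**The drift model is simplistic.** Resets would interrupt drift, and clinically triggered RHCs need not be evenly spread. This stands, and it is why the fractions are illustrations.

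**Other tables are unsplit too.** Demographics, compliance and medication changes also lack time columns. This is true, so inconsistent layout is not the argument. The argument is that accuracy over time is the question and nothing else answers it.

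**A split may leave few pairs, and late RHCs come from selected patients.** Both stand and limit what the fix can show.

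**Conclusion.** The concern holds as a gap in the visible text. Sensor accuracy is planned only as a Bland-Altman of sensor against catheter, without time since implant, a repeated-measures method, or a rule for resets and implant-day pairs. No planned analysis estimates drift in a sensor that still transmits.

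If the pairs were summarized without regard to time, the pooled bias would show about half of a common month-24 drift, or about a quarter if the mean RHC time were 6 months. Drift of mixed sign would show no mean bias and only partly widened limits. These fractions assume linear drift and no resets, and the half also assumes evenly spread RHCs. The amounts in mmHg depend on assumed drift rates. The documents do not show that drift occurs; allowing baseline resets shows only that an offset is anticipated.

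This is a descriptive report item. It affects no primary endpoint, hypothesis or decision rule, so the improvement is worthwhile but modest.

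**What to change.** In the Sensor Performance block of Appendix L:

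1. Fit a mixed model of the sensor-minus-catheter difference on time since implant with a patient random effect. Add time since the last baseline setting where the data allow.
2. Report bias and repeated-measures (variance-component) limits of agreement by time since implant. Use the 6-month periods of the neighbouring tables if there are enough pairs, and otherwise merge them, for example 0–12 and >12–24 months.
3. Show implant-day calibration pairs separately from later pairs.
4. State how pairs before and after a reset are handled.
5. State that the time trend is descriptive, because RHCs are done only when clinically warranted and late pairs come from selected patients.

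The cost is table-shell wording and programming. The pairs and their dates should already be available, and no extra catheterization is needed. The downside is wider limits in each period, since each holds fewer pairs.

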Appendix M: Schematic Diagram of Main PAS Study and Substudy

This confidential document is the property of Abbott and shall not be reproduced, distributed, disclosed or used without the express written consent of Abbott

Clinical Investigation Plan
